4.2 Assessments and Procedures

4.2.1 Study Conduct

The study will be done in five cohorts of 60-70 subjects each for logistical reasons. The first cohort will be conducted in the Spring of 2016. Subsequent cohorts will be done in Fall 2016, Spring 2017, Fall 2017 and Spring 2018. The assays and data collection for analysis of the primary and secondary efficacy endpoints will be substantially complete by December, 2018.

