6.4 Exploratory endpoints

6.4.1 Cytokine response of nasal mucosa

6.4.1.1 Interleukin-8 assay: Concentrations of interleukin-8 in nasal lavage are determined with a commercially available ELISA assay (R&D Systems, Minneapolis, MN). The lower limit of detection for the assay is 31.25 pg/mL. The precision of the assay for measurement of IL-8 in nasal wash has been determined with pools of nasal wash spiked with known concentrations of IL-8. Intra-assay variability was found to range from 3.8-5.7% and inter-assay variability was found to range from 2.7-11% for nasal wash containing high and low concentrations of IL-8, respectively. The recovery of IL-8 in nasal wash ranged from 88-136% of predicted. Specimens that have IL-8 concentrations greater than the operating range of the assay will be diluted 1:10 and 1:100 and re-assayed.

6.4.2 *Multiplex assays: A panel of cytokines and chemokines (TGF- β 1, GCSF, GMCSF, IFN- γ , IL-1 α , IL-12p70, IL-15, CCL20, IL-1 β , IL-6, IL-10, CXCL10, CCL2, CCL3, CCL5, TNF- α) may be measured in nasal lavage fluid using a commercially available multiplex assay (Aushon BioSystems, Inc., Billerica, MA). A determination of which assays will be included will be made as a post-hoc exploratory analysis. Blood transcriptomics*

6.4.2.1 Collection of specimens: The effect of probiotics on gene expression before and after rhinovirus challenge will be determined by comparing expression in the probiotic and placebo groups on study days -28, 0 and 2. Expression analysis will be done on peripheral blood specimens by microarrays targeted at inflammatory and antiviral genes. Blood samples will be collected in PAXgene RNA tubes (PreAnalytix) and stored at -80°C until shipping. Samples will be shipped on dry ice to DuPont Haskell Global Centers for Health and Environmental Science and immediately stored at -80°C until further processing. RNA will be isolated from blood stored in PAXgene tubes using a PAXgene Blood RNA isolation kit (Qiagen) and potential DNA contamination will be removed with on-column DNase treatment. RNA concentration and quality will be verified on a Nanodrop® spectrophotometer (NanoDrop) or with a Quant-iT™ RiboGreen® RNA Assay Kit (Thermo Fisher). RNA integrity will be determined with an Agilent Bioanalyzer 2100 (Agilent). All RNA samples processed for RNA-sequencing should have a 260/280 absorption ratio greater than 2 and a RNA integrity number (RIN) greater than 9.8.

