6.4.2.2 RNA-seq: Targeted RNA-seq library preparation will be conducted with Tempo-Seq (BioSpyder) detector oligos designed against a ~1500 human gene panel focused on innate immunity and antiviral defense genes. Library preparation will be conducted in 96 sample batches. Up to 2 library preparations (n=192 samples) will be pooled, purified, quantitated and stored frozen prior to RNA-sequencing. The pooled libraries will be sent to the Pioneer core genomics facility in Johnston, Iowa for RNA-seq using an Illumina NextSeq, or HiSeq platform. The target read-depth per sample will be 1.5 million reads to ensure 500-1000 reads per gene. The reads will be quality filtered, trimmed and demultiplexed by the technical staff in Johnston. The resulting FASTQ files will be transferred via external hard drive, or through the DuPont network for further processing. Backup FASTQ files will be archived at the Johnston facility. The FASTQ files will be aligned to an annotated reference to determine the number of reads per gene. The reads will be quantitated by

normalizing with control genes in the samples set. Other quantitation methods may be considered as well. Data will be stored in this format until the samples can be decoded for further analysis. Once decoded, metadata will be added to the data files to add additional annotation to the sample identifiers and group samples according to experimental conditions. Differential expression analysis will be conducted to determine transcripts that are up or down regulated between the experimental conditions.

6.4.3 *Rhinovirus type-specific antibody response*

6.4.3.1 The effect of probiotic on host antibody responses to the challenge virus will be determined by comparing the convalescent neutralizing antibody titer in the probiotic and placebo groups.

6.4.4 *Fecal, throat and nasal microbiota*

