### Blood transcriptomics

For blood transcriptomics at least the following analyses will be conducted. The PP population will be primarily used.

Unsupervised clustering of the samples will be conducted. Clustering will be done at DuPont and in case clusters are formed, the clustering information (per sample per subject) will be provided to 4Pharma for further the analyses described below.

- Timepoint and treatment effect on clustering will be investigated with categorical repeated measures models, where clustering is the outcome variable, and timepoint, treatment, interaction of treatment and timepoint are included as fixed effects.
- Effect of cohort, infection (yes/ no) and illness (yes/ no) on clustering will be investigated with the above described model by including separately each factor to the analysis model.
- The effect of D-28/D0 clustering on the following outcome variables will be investigated by adding the cluster as a fixed effect to the analysis models: Duration of illness, viral shedding, clinical symptom severity score and immune markers. For symptom scores, the analysis models have already been described in 11.2.5 and 11.2.6. Also, for immune markers the analysis model to be used has already been described in this chapter. For duration of illness an analysis of covariance (ANCOVA) model will be used including treatment and cluster effect in the model. The analysis will be conducted using the Ill population. For viral shedding a logistic regression model with treatment and cluster effect will be fitted and infected population used. For all models, also fixed interaction effect of treatment and cluster may be investigated.

In addition to the clustering, correlations between individual genes from throat and nasal metagenomics will be calculated, if feasible. For the correlations FDR correction will be used with the p-values.

Connections between the exploratory data/ results and efficacy and other endpoints may be investigated with suitable analysis models (will be described in the Documentation of the Statistical Methods, if done). Part of the exploratory analyses (microbiota and transcriptomics) will not be included in the Statistical Study Report.

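### Exploratory models use transcriptome clusters to predict illness outcomes without a cohort term, so a cohort difference could pass as a cluster effect

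*Protocol*

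**What the plan says.** **Cohorts.** Protocol 4.2.1: "The study will be done in five cohorts of 60-70 subjects each for logistical reasons". The first was planned for Spring 2016, and "Subsequent cohorts will be done in Fall 2016, Spring 2017, Fall 2017 and Spring 2018".

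**Samples and laboratory batches.** Protocol 6.4.2.1 plans the transcriptome analysis by "comparing expression in the probiotic and placebo groups on study days -28, 0 and 2", so each subject gives three samples. Protocol 6.4.2.2 then states "Library preparation will be conducted in 96 sample batches. Up to 2 library preparations (n=192 samples) will be pooled". It plans normalisation to control genes and leaves other quantitation methods open. It gives no rule for allocating samples to batches or pools.

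**Clusters as predictors.** SAP 11.3 has the sponsor's laboratory cluster the samples, without describing the method, and then adds the Day -28/Day 0 cluster as a fixed effect to the outcome models:
- Duration: "For duration of illness an analysis of covariance (ANCOVA) model will be used including treatment and cluster effect in the model".
- Shedding: a logistic model, also with treatment and cluster.
- Symptom scores: the models of SAP 11.2.5 and 11.2.6, which follow 11.2.3 (treatment, day, their interaction, random subject).
- Immune markers: the IL-8 model, with treatment, baseline value, timepoint, treatment by timepoint and random subject.

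None of the four contains cohort or batch.

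**Where cohort does appear.** SAP 7.1 makes it a subgroup factor for the primary endpoint, and SAP 11.4 lists it among potential confounders in the sensitivity analysis of that endpoint. For the clusters, SAP 11.3 states: "Effect of cohort, infection (yes/ no) and illness (yes/ no) on clustering will be investigated with the above described model". There the cluster is the outcome.

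**The concern.** Cohort could be a common cause of the predictor and the outcome. The SAP treats it as a possible driver of clustering and as a potential confounder of illness incidence, yet leaves it out of the models that link cluster to outcome. Two routes are plausible, though the documents give neither a size nor direct evidence. Blood expression may differ between seasons or between library batches. Outcomes may differ between cohorts, for example because the inoculum may range from 20 to 100 TCID50 (Protocol 4.2.10).

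If both links exist, a cluster that mainly marks which cohort a subject joined will appear to predict illness duration or immune response. The study would then report a transcriptome profile as prognostic when it carries no information beyond cohort. The planned test of cohort on clustering would warn of this, but the SAP does not say what follows from a positive result.

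**Working it through.** **1. Batch and pool sizes against cohort sizes**
- Pool: 2 x 96 = 192 samples, which agrees with the protocol's figure. At three samples per subject this is 192 / 3 = 64 subjects.
- A cohort of 60 to 70 subjects gives 180 to 210 samples, so a full pool is 192/210 = 0.91 to 192/180 = 1.07 cohorts.
- Five cohorts of 60 to 70 would be 300 to 350 subjects. Protocol 4.1.1 plans 2 x 130 = 260 treated, and SAP 4 gives 254 challenged. Spread evenly, 254 / 5 = 50.8 subjects or 152.4 samples per cohort, so a pool is 192/152.4 = 1.26 cohorts.
- In total, 254 x 3 = 762 samples make 762/192 = 4.0 pools, against five cohorts.
- Suppose cohorts of 51, 51, 51, 51 and 50 were processed in study-number order. Pool 1 would hold cohort 1 and 13 subjects of cohort 2. Pool 2 would hold 38 of cohort 2 and 26 of cohort 3. Pool 3 would hold 25 of cohort 3 and 39 of cohort 4. Pool 4 would hold 12 of cohort 4 and all of cohort 5. Cohorts 2, 3 and 4 would each straddle two pools.

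Pool and cohort are therefore similar in size (about 0.9 to 1.3 cohorts per pool), but the documents do not make them the same factor.

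**2. Effect of leaving cohort out of the duration model**

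Inputs from the documents: five cohorts; 95 completed subjects per arm; illness in 60% and 40% (Protocol 8.1). Expected ill subjects: 95 x 0.60 + 95 x 0.40 = 57 + 38 = 95.

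Assumptions, not in the documents: equal cohorts, two clusters, residual SD of 3 days, and no true cluster or treatment effect. Cohort means vary with SD 0, 0.75 or 1.5 days. The cluster-cohort link is none, moderate (membership 70% in two cohorts, 37% in the other three) or strong (90% and 23%).

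Models: duration on treatment + cluster, as in SAP 11.3, and the same with cohort as a fixed effect. The table shows how often the cluster term had p < 0.05 in 2,000 simulated trials per row. The simulation standard error near 5% is sqrt(0.05 x 0.95 / 2000) = 0.5 percentage points.

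| Cluster-cohort link | SD between cohorts (days) | Without cohort | With cohort |
|---|---|---|---|
| None | 0 | 4.5% | 4.9% |
| None | 0.75 | 4.2% | 4.6% |
| None | 1.5 | 4.6% | 4.6% |
| Moderate | 0 | 4.4% | 4.2% |
| Moderate | 0.75 | 6.9% | 4.5% |
| Moderate | 1.5 | 8.9% | 3.9% |
| Strong | 0 | 4.6% | 5.5% |
| Strong | 0.75 | 10.6% | 5.2% |
| Strong | 1.5 | 23.0% | 4.9% |

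Inflation needs both links. Where both are present, the rate is 6.9% to 23.0% without cohort and 3.9% to 5.2% with it.

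**3. Would the planned check notice?**

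In the same simulations, a chi-square test of cluster by cohort was significant in about 74% of trials under the moderate link and in all trials under the strong link. It stands in for the SAP's repeated-measures model, which would use more subjects. The check would usually flag the problem, but it leaves the outcome models unadjusted.

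**The case against.** The strongest reply is that the SAP already provides the diagnostic. A cohort-driven cluster would be seen before anyone interpreted it, and SAP 11.3 lists only a minimum set of analyses. That stands as far as detection goes. It does not say what happens next, and it does not cover batch.

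Second, control-gene normalisation may remove part of a technical batch effect, and the baseline covariate in the immune-marker models absorbs part of any baseline cohort difference. Both points stand. Neither deals with a seasonal difference in the duration or shedding models, which have no other covariate.

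Third, a seasonal immune state is biology, and adjusting for cohort removes that signal too. This is fair, and it is why the unadjusted estimate should be kept beside the adjusted one.

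A reader might go further in three ways that the documents do not support:
- **That each pool is one cohort, so the two effects cannot be separated.** The sizes invite this, but processing order is not stated, and the subject numbers give four pools against five cohorts.
- **That false positives could reach about 69%.** With 48 ill subjects per cluster and SD 3 days, Phi(d / (3 x sqrt(2/48)) - 1.96) gives 13%, 37% and 69% for differences of 0.5, 1 and 1.5 days. The arithmetic is right, but it assumes that the clusters follow the cohorts or pools completely.
- **That a stated study objective is at risk.** Protocol 2.2.3 names the probiotic's effect on the transcriptome, and correlations of microbiome profiles and immune responses with illness. It names no objective linking transcriptome profile to illness.

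**Conclusion.** The point holds as a modest gap in exploratory analyses. A factor that the SAP itself suspects on both sides is missing from every model that uses a transcriptome cluster as a predictor, and the planned check has no stated consequence. Under the assumptions above, the false-positive rate of the cluster term is about 7% to 23% without cohort and about 5% with it. The range is illustrative, because the documents give neither the cluster-cohort link nor the cohort difference in duration. Cohort is listed as a confounder for illness incidence, not for duration. Confounding of cohort with library batch or pool remains possible but is not documented. The primary chi-square test and the randomised treatment comparison are not affected.

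**What to change.** In SAP 11.3, add cohort as a fixed effect to every model that uses the Day -28/Day 0 transcriptome cluster as a predictor (duration, shedding, symptom scores, immune markers). Report the result without cohort alongside, and say that the adjusted estimate is a within-cohort one. The cost is 5 - 1 = 4 degrees of freedom per model, and the term can be added even if the laboratory work is finished.

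In Protocol 6.4.2.2, record the library batch and pool of each sample. For samples not yet processed, keep each subject's three samples in one 96-sample batch (96 / 3 = 32 subjects) and balance cohorts across batches. Adjust for batch where it is not aliased with cohort. This needs a plate layout but no extra samples or assays. Balancing across cohorts means holding frozen samples until later cohorts are collected. The December 2018 date in Protocol 4.2.1 covers only the primary and secondary efficacy endpoints, so it does not stand in the way.

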7.1.2 Assessment of Adverse Events

For the purposes of this study using experimental rhinovirus infection, physical signs and symptoms that are expected to be associated with the common cold should not be reported as adverse events. The following physical signs and symptoms are expected to be associated with the common cold: nasal obstruction (nasal stuffiness), coryza (runny nose), sore throat, cough, sneezing, myalgia, headache, feverishness, chills, loss of appetite and malaise.

Information regarding common cold-related complications must be documented appropriately. Common cold-related complications include bronchitis, bronchospasm or exacerbation of asthma, sinusitis and otitis media. For common cold-related complications, the following information should be documented: onset date, severity, seriousness, relationship to study therapy, action taken regarding study therapy, outcome, and therapy given for event.

Some subjects may experience gut discomfort during the study product consumption. The symptoms that have been associated with use of bifidobacteria include bloating, flatulence and abdominal pain. The subjects should contact the study staff in the case that symptoms persist.

Assessment of all adverse events will include recording the time of onset and resolution of the event, severity, intervention, and an attribution by the investigator of whether the event was related to the study product.

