Reference	Number and characteristics of subjects consuming BI-04	Supplementation dose and length	Adverse events
[name] et al. 2015; Unpublished	95/190 Adults (Mean 22 yrs)	2×10^9 CFU/d for 32 d	Gastrointestinal AEs occurred only in the active group ($P < 0.01$). AEs in 5 subjects (4 GI, 1 Respiratory illness) were judged, prior to unblinding, to be possibly or probably related to the study interventions.
[5, 6, 14]	161/465 Adults (average 36 y) Physically active	2×10^9 CFU/d for 150 d	2 subjects withdrew because of uncomfortable GI symptoms
[15]	336/503 Adults (30-70 y) Receiving antibiotics	4.3×10^9 CFU/d (n=168) or 1×10^9 CFU/d (n=168) in a mixture of four strains for 10 to 21 d	AE rates were 7.2%, 4.2% and 4.2% in the placebo, high-dose and low-dose groups, respectively (AEs were allergy to sea food, arrhythmia, fever, headache, left upper arm fracture, runny nose and vomiting) One SAE was reported (death due to myocardial infarction; the subject had a history of coronary heart disease) None of the AEs were considered to be related to the study product High-dose probiotic group had fewer drop-outs than low-dose or placebo group
[16]	24 / 47 Children (mean 9 yrs) with history of allergy	1.25×10^9 CFU/d with one other strain for 122 d	2 subjects dropped out in probiotic group, no reason published
[17]	20/40 Adults (18-45y) Consuming antibiotics	1×10^{10} CFU/d in a mixture of five strains for 20 d	No significant difference in AE rate between treatment groups (both groups consumed antibiotics) Most common AEs were diarrhea (3 in active and 1 in placebo group), vaginal yeast infection (4 in active and 1 in placebo group) and abdominal pain (3 in probiotic and 3 in active group)
[18]	9/86 Adults (18-64 y) Oral cholera vaccine given	2×10^{10} CFU/d for 3 w	None documented
[19]	20/40 Adults (>18y) Consuming antibiotics	5×10^9 CFU/d in a mixture of five strains for 20 d	None documented
[7]	9/18 Healthy elderly	3.5×10^{10} CFU/d in a mixture with inulin and Bb-02 for 28 days	None documented

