4.2.11 Symptom scoring (Study Days 0-14)

Symptom scores on study days 0-5 will be collected in an interactive interview with the study staff. Symptoms will be assessed using the modified Jackson criteria. On study days 6-14, volunteers will be asked to complete a symptom diary that will consist of the same symptoms assessed by the Jackson criteria. Volunteers will also be asked whether their symptoms affected their physical activity.

5 Study Product

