5.3 Dosage and Administration

5.3.1 Duration of Treatment

All volunteers will sign consent and be screened for study eligibility before randomization to study product. On day -28 of the study, all volunteers will come to the study site, be randomized to study treatment and instructed when to take the first dose of study product. Volunteers will be instructed to take daily one sachet of the study product mixed into a drink that is not hot and does not contain alcohol. The study product will have a minimal of 2×10^9 cfus of BI-04. On days -21, -14 and -7 subjects will come to the study site for re-supply of the probiotic and for evaluation of compliance. On day 0 the volunteers will be challenged with the study virus. After the virus challenge all volunteers will continue the study treatment on through study day 14.

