6.4.4.1 Bacterial DNA will be isolated from the swabs and feces by using MagMAX™ Total Nucleic Acid Isolation Kit (Applied Biosystems, Bridgewater, NJ). Human DNA may be quantified for analysing the ratio of human and bacterial DNA by using housekeeping genes that do not allow subject identification. The composition of microbiota will be analyzed by next-generation sequencing (or equivalent) technology for identification of microbial species in the samples. The data will be analyzed to determine effects of probiotic on both abundance and diversity of bacterial species. . In addition, single strain targeting PCR-based molecular methods (i.e. qPCR, digital PCR or equivalent) will be applied to detect the supplemented probiotic strain, BI-04.

6.4.4.2 Throat swabs will be collected on study days 0, 5, and 14 for detection of pharyngeal pathogens by culture and qPCR. A single swab will be sent to the microbiology laboratory at the University of Virginia for detection of *S. aureus*, pneumococcus, *H. influenza*, meningococcus and group A streptococcus.

6.4.5 *Cold questionnaire comparison*

Performance of the questionnaire used in the West study [5] will be compared to endpoints of this study.

6.5 **Assessment of safety**

6.5.1 *Adverse events*

6.5.1.1 The safety of the study interventions will be assessed by monitoring of adverse events. Volunteers will be asked at each study visit to report any unexpected events whether or not they are apparently study related. Each event will be recorded and an assessment of relatedness to the study interventions will be made by the investigator. Adverse events will be coded according to established standards (MedDRA). The analysis will compare both total and related events in the probiotic and the control group.

7 **Adverse Events**

7.1 **Adverse event**

7.1.1 *Definitions*

7.1.1.1 An adverse event (AE) is any untoward, undesired, or unplanned event in the form of signs, symptoms, disease, or laboratory or physiologic observations occurring in a

person given an IP in a clinical study. The event does not need to be causally related to the IP or the clinical study. An AE includes, but is not limited to the following:

- Any clinically significant worsening of a pre-existing condition.
- An AE occurring from overdose of an IP, whether accidental or intentional. Overdose is a dose greater than specified in the protocol.
- An AE occurring from abuse (e.g., use for non-clinical reasons) of an IP.

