7.1.3 Halting rules for adverse events

Should any of the following occur, the entire study will be stopped

- B1-04 bacteremia or invasive infection
- Any single serious and unexpected adverse event for which attribution is assessed as possibly, probably, or definitely related to the study products.
- 10% of participants develop any severe (grade 3) gastrointestinal AE
- 10% of participants develop any severe (grade 3) non-gastrointestinal AEs of the same type.

7.1.4 *Monitoring of adverse events*

All volunteers will be specifically asked about any unexpected medical events at each study visit after the study treatment is begun. All volunteers will be instructed to contact the study site if they experience any unexpected symptoms during the time they are consuming the study product. At the final study visit, volunteers will be asked if they have had any unusual symptoms or problems during the study. All positive responses will be recorded. Medically significant responses will be followed until the symptom/problem is resolved or judged unrelated to the study and the subject has been referred for appropriate care.

7.2 **Serious adverse events and unexpected**

7.2.1 *Definitions*

7.2.1.1 General definitions:

A Serious Adverse Event (SAE) or Serious Adverse Drug Reaction (ADR) is any untoward medical occurrence that at any dose:

- Results in death.
- Is life-threatening (see below).
- Requires inpatient hospitalization or prolongation of an existing hospitalization (see below).
- Results in a persistent or significant disability or incapacity (see below).
- Results in cancer.
- Is a congenital anomaly or birth defect.

Additionally, important medical events that may not result in death, be life-threatening, or require hospitalization may be considered SAEs when, based on appropriate medical judgment, they may jeopardize the subject and may require medical or surgical intervention to prevent one of the outcomes listed in this definition. Examples of such events include allergic broncho-spasm requiring intensive treatment in an emergency room or at home, blood dyscrasias or convulsions that do not result in hospitalization, or development of drug dependency or drug abuse.

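### The rule that cold symptoms are not adverse events (Protocol 7.1.2) is not limited to the period after inoculation, so as written it also applies to 28 of 42 product days before any virus is given

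*Protocol*

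**What the plan says.** Protocol 7.1.2 opens by referring to the experimental infection and then says that "physical signs and symptoms that are expected to be associated with the common cold should not be reported as adverse events". The listed symptoms are nasal obstruction and runny nose, followed by "sore throat, cough, sneezing, myalgia, headache, feverishness, chills, loss of appetite and malaise": eleven in all. The section gives no onset window and does not mention the challenge day.

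Other parts of the plan bear on this:

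- **Timing of product and virus.** Under Protocol 5.3.1, product starts at the Day -28 visit and continues through Day 14. The virus comes in between: "On day 0 the volunteers will be challenged with the study virus".
- **Symptom scoring.** Protocol 4.2.11: "Symptom scores on study days 0-5 will be collected in an interactive interview with the study staff". A diary covers Days 6 to 14. Nothing is scored before Day 0 or after Day 14.
- **AE questioning.** Protocol 6.5.1: "Volunteers will be asked at each study visit to report any unexpected events whether or not they are apparently study related". Protocol 7.1.4 likewise asks about unexpected events at each visit once treatment has begun. AE assessments are scheduled on Days -21, -14, -7 and 0, after challenge, and at a final visit (Day 21-30 in 4.2.2).
- **AE definition.** Protocol 7.1.1 counts any untoward sign or symptom in a person given the product, whether or not the product caused it.
- **Halting rules.** One trigger in Protocol 7.1.3 is "10% of participants develop any severe (grade 3) non-gastrointestinal AEs of the same type".
- **Analysis.** SAP section 2 names safety and tolerability among the secondary objectives. SAP 13.1 tabulates AEs by arm and applies Fisher's exact test to those reported by more than 5% of either arm. No split by onset before or after challenge is planned.

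**The concern.** The exemption has a sound purpose. After inoculation, cold symptoms are the efficacy outcome, and entering them as AEs as well would fill the safety tables with the induced illness. That reasoning does not reach the four weeks before inoculation, when no induced cold exists and no symptom instrument is running. A headache, chills or malaise on Day -20 meets the definition in 7.1.1, but 7.1.2 says not to report it.

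This matters because the pre-challenge weeks are the only time on product without symptoms from the experimental infection. A tolerability difference between arms would be easiest to see there.

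The protocol's own safety background shows that such events can occur. Section 1.3 reports that in the earlier challenge trial "AEs in 5 subjects (4 GI, 1 Respiratory illness) were judged, prior to unblinding, to be possibly or probably related" to the study interventions. Table 1 also lists fever, headache and runny nose among AEs in a trial of a mixture that included this strain, although none was considered product-related there.

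**Working it through.** **Inputs.** First product day: Day -28. Challenge: Day 0. Last product day: Day 14 (all Protocol 5.3.1). Stated treatment length: 42 days, with 130 subjects per arm (4.1.1). Window on the Day -28 visit: ± 4 days (4.2.2). Scored period: Days 0 to 14 (4.2.11).

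**The plan's figure.** 14 − (−28) = 42 days, which matches 4.1.1.

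**Share of product days before challenge.** 0 − (−28) = 28 days, and 28 / 42 = 66.7%. With the visit window this runs from 24 / (24 + 14) = 63.2% to 32 / (32 + 14) = 69.6%.

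**Exposure affected.** If all 2 × 130 = 260 subjects take product for 28 days, 260 × 28 = 7,280 person-days. For the 254 challenged subjects in SAP section 4, 254 × 28 = 7,112. These measure exposure time. The documents give no rate for these symptoms, so the number of events lost cannot be estimated.

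**After Day 14.** The final visit falls on Day 21 to 30, so 7 to 16 days of follow-up after the last dose have AE assessment but no symptom score.

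**Coverage by period, following 7.1.2 literally:**

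| Period | On product | AE assessment | Listed symptoms reportable as AEs | Symptom score |
|---|---|---|---|---|
| Day -28 to Day -1 | yes | yes | no | no |
| Day 0 to Day 14 | yes | yes | no | yes |
| After Day 14 to final visit | no | yes | no | no |

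**Is every listed symptom scored in the middle row?** The documents do not set out the modified Jackson items. SAP 11.3 names obstruction, rhinorrhea, cough and sore throat, and SAP 20.2 adds sneezing as an example. That accounts for 5 of the 11. The other 11 − 5 = 6 (myalgia, headache, feverishness, chills, loss of appetite, malaise) are nowhere named as scored, so their capture on Days 0 to 14 cannot be confirmed from these documents.

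**Consequence for SAP 13.1.** With 130 per arm, 5% is 0.05 × 130 = 6.5, so an AE needs at least 7 subjects in one arm to be tested. A symptom that is never reported as an AE cannot reach that threshold.

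**Do other sections limit the rule?** No section of either document ties it to inoculation. Sections 6.5.1 and 7.1.4 ask mainly about *unexpected* events, while 7.1.2 calls the listed symptoms *expected*. Staff could follow either text, and the documents do not say which governs.

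**The case against.** The strongest reply is that the opening words of 7.1.2 tie the exemption to the induced cold, so that before inoculation nothing is expected and nothing is exempt. Section 7.1.4 supports this. Volunteers are to contact the site about unexpected symptoms while taking product, the final visit asks about anything unusual during the study, and positive answers are recorded. This is a reasonable reading, and some staff may have worked that way. It stands as a reason not to claim that the data are certainly lost. It does not settle the matter, because the sentence states no period and its list is unconditional.

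A reader might infer several stronger points that the documents do not support:

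- **That these events leave no record.** Serious events are reportable from consent to the end of the trial (7.2.4). Complications such as bronchitis and sinusitis must be documented (7.1.2). Concomitant medication is reviewed at each pre-challenge visit. Upper respiratory infection in the two weeks before challenge is reviewed on Day 0, though that leaves the first 28 − 14 = 14 product days uncovered. These are partial traces, and none yields an AE rate by arm.
- **That measured fever or respiratory illness is exempt.** The list says feverishness, and it is a list of symptoms. For the earlier trial's respiratory event, the protocol does not say whether it came before or after challenge.
- **That the virus confounds the safety comparison, or that the rule biases it.** Both randomised arms are challenged under blinding and the rule applies to both equally. The loss is one of sensitivity.
- **That the halting rules are disabled.** Bacteremia or invasive infection is a separate trigger that does not depend on chills being logged as an AE. Only the 10% non-gastrointestinal rule depends on what counts as an AE.

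**Conclusion.** The point holds as a gap in safety ascertainment. As written, 7.1.2 takes eleven non-serious symptoms out of AE reporting for 28 of 42 product days (67%; 63% to 70% with the visit window) and for 7 to 16 days of follow-up after Day 14. No symptom score replaces AE reporting in either period. The size rests on a literal reading of 7.1.2 and on nominal dosing. If sites read the rule as starting at inoculation, the actual loss is smaller, but the plan does not tell them to.

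The effect is under-recording in both arms during the one on-product period free of experimental cold symptoms. No efficacy endpoint is affected. It is worth correcting because safety and tolerability is a stated secondary objective and the correction is small.

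**What to change.** 1. In Protocol 7.1.2, state that the exemption applies only to symptoms with onset after inoculation on Day 0 through Day 14, and only to those actually scored in that window. Name the scored items. Record the listed symptoms as AEs outside it.
2. In SAP 13.1, add a table of AEs by arm, split by onset before and after challenge. Section 7.1.2 already requires the time of onset, so no new data item is needed.
3. Reconcile 7.1.2 with 7.1.1, 6.5.1 and 7.1.4 so that *expected* and *unexpected* have one meaning. Reconcile it also with 7.1.3, so that it is clear which events count as AEs for the 10% non-gastrointestinal rule. How the halting rules operate is for the sponsor and the investigator to decide.

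**Cost.** One sentence, one table and a few more mild AE entries. Protocol 4.2.1 plans five cohorts from Spring 2016 to Spring 2018, and version 5.0 is dated October 2017. A change made at that stage would leave AE capture different between earlier and later cohorts, and the study report should say so. For cohorts already completed, the report should state how sites applied 7.1.2 before challenge.
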